## 7.5 Hy's Law

The Hy's Law is used in this study to monitor any possible drug-induced liver injury. The Hy's Law usually means that AST or ALT $> 3\times\text{ULN}$  and TBiL $> 2\times\text{ULN}$ , non-biliary increase (usually alkaline phosphatase  $< 2\times\text{ULN}$ ) without any other diseases for explanation of the increase. If ALT or AST is  $> 3\times\text{ULN}$ , and TBiL is  $> 2\times\text{ULN}$  without any other previous diseases for explanation of the increase, no matter whether alkaline phosphatase (ALP) increases or not, the Investigator must inform the subject of the central laboratory reports within 48 hours after awareness and ask the subject to return to the study site for central laboratory re-evaluation (if necessary, re-examinations at local laboratories can be taken). The Investigator conducts re-evaluation and closely monitors or follows-up with the subjects, or stops the study medications according to the Section 4.5.3 Subject withdrawal due to abnormal liver function and Appendix 6: Measures to be Taken for Abnormal Liver Functions in the protocol. The Investigator evaluates the etiology and conducts every essential examination to rule out drug-induced liver injury. If the Investigator confirms the event meets Hy's Law, the event needs to be reported as an SAE.

## 7.6 Post-study AE Reporting

At any time after the study ends, if the Investigator is informed of any AE which is considered possibly related to the study medication, the Investigator needs to promptly report the event to the Clinical Drug Safety department of the Sponsor. The follow-up information of the SAEs after database lock also needs to be reported to the Clinical Drug Safety department of the Sponsor. The contact information is: Email: [[contact]](mailto:[contact]), [contact], [contact].

## 7.7 Lack of Efficacy or Aggravation of T2DM

The events that are apparently consistent with expected progression of T2DM (e.g., hyperglycemia) do not need to be recorded as AEs. These data is used for efficacy assessment (parameters for glycemic control).

The protocol defines the withdrawal criteria relevant to poor glycemic control/hyperglycemia (see Section 4.5.2 withdrawal criteria due to hyperglycemia and Appendix 4 SMBG Procedures). The Investigator must warrant no other causes for poor glycemic control except for lack of efficacy (e.g. concurrent acute inflammations/infections, and concomitant treatments, etc.). If the disease aggravation is unexpected, it should be reported as an AE. The Investigator is suggested to give the subjects relevant examinations to find out the reason for disease aggravation and record the reason on eCRF.

## 7.8 Laboratory Safety Assessments

Blood and urine samples are collected for laboratory assessments. The collecting date and time are recorded on the laboratory tests application form. The samples are processed in the central laboratory and the results are reported to study sites within 72 hours.

All subjects are suggested to go to each visit in fasting state between 7:00 am and 10:00 am. The subjects should be informed to avoid heavy physical activities and intake of high fat and high calorie food one day before the visit. Food and beverage except for water are prohibited within 8 hours before the visit. Also, the subjects are informed of not taking the study medications by themselves in the morning of the visit day. Other permitted medications can only be administered with water.

All samples are collected by authorized study staffs, and processed per manuals in the central laboratory. The latest laboratory reference range is provided to study sites during the study. The laboratory results are compared with the reference range values. Results exceeding the normal range are marked. The Investigator evaluates the abnormal results and decides whether they are clinically significant or not.

See Section 7.1.3 for how to record and report AEs relevant to laboratory tests.

The following laboratory safety parameters are measured:

- Hematology: hemoglobin, hematocrit, erythrocytes count, leukocytes count, neutrophils, basophils, eosinophils, monocytes, lymphocytes, and platelet count
- Urinalysis: pH, specific gravity, protein, glucose, erythrocytes, leukocytes, and ketone bodies
- Blood biochemistry: glucose, total bilirubin, ALT, AST, gamma-glutamyl transferase, alkaline phosphatase, albumin, total protein, lactate dehydrogenase, urea nitrogen, creatinine, uric acid, sodium, potassium, chloride, calcium, creatine kinase, creatine kinase isoenzyme, total cholesterol, high-density lipoprotein cholesterol, low-density lipoprotein cholesterol, and triglyceride.

All methods, instruments, and quality control requirements for laboratory tests are described in detail in the manual of central laboratory.

## 7.9 Physical Examination

Full physical examination is conducted at each visit except Visit 2, Visit 3 and Visit 16. The physical examination includes a check on: general appearance, head and neck, chest (heart and lung), abdomen, and limbs.

Any finding from physical examination at subsequent study visits is compared with the results at screening visit and is evaluated for clinical significance. See Section 7.1.3 AEs Related to Examinations and Laboratory Tests for how to record and report AEs related to examinations.

## 7.10 12-lead ECG

A 12-lead ECG examination is conducted at each visit except Visit 2 and Visit 16. The Investigator evaluates the ECG results and records the results on eCRF as “normal” or

“abnormal with/without clinical significance”. See Section 7.1.3 AEs Related to Examinations and Laboratory Tests for how to record and report AEs related to laboratory examinations.

## 7.11 Vital Signs

Vital signs (blood pressure, pulse rate, respiratory rate and body temperature) are measured according to study protocol. Height and body weight are included as part of vital sign assessments.

The subjects should rest for at least 5 minutes before vital sign assessments. Throughout the study, all efforts are made to measure pulse rate and blood pressure from the same arm. The arm used for measurement is documented in the original records.

### Pulse rate

Palpation on the radial artery is suggested to last for at least 30 seconds to calculate the number of beats per minute, which is recorded on eCRF. If necessary, palpation is on bilateral radial artery simultaneously to check the symmetry. It is recommended to be marked on eCRF if there is any asymmetry.

### Body temperature

A thermometer is placed at deep axillary region of the subjects. The subjects are told to hold the thermometer tightly and read the temperature 10 minutes later. Be noted that there should not be heating or cooling objects at the axillary region and sweat at the axillary region should be swiped.

### Respiratory rate

The subjects are observed for breathing rhythm and breathing frequency per minute is recorded.

### Blood pressure

A mercury sphygmomanometer is used for measuring blood pressure. The subject should be in a quiet place with his feet flat on the floor back against the chair. Cigarettes and coffee is prohibited and bladder is emptied within 30 minutes before the assessment. The subject's upper arm is exposed and stretched slightly with the elbow at the same height with heart. The cuff is closely and evenly wrapped around upper arm with its lower edge at about 2.5 cm above the antecubital fossa and the center of cuff at the surface of brachial artery. After touching the brachial artery, the examiner puts the stethoscope's bell over the brachial artery for auscultation. Then the cuff is inflated while auscultation. After the sound of brachial artery pulse disappears, the cuff continues to be inflated until the reading values increase for additional 30 mmHg. Then the cuff is deflated gradually (2–6 mmHg/s). Eyes are kept at the same level with the mercury gauge while the mercury column is descending, and blood pressure is read according to auscultation. Blood pressure is measured at least twice with two-minute interval and the average of the two measurements is calculated. If the difference of the two measurements in systolic or

diastolic blood pressure is larger than 5 mmHg, a third measurement is done after 2 minutes and the average of 3 measurements is calculated.

## **Height and Weight**

Shoes and thick clothes should be taken off while height and body weight are being measured. The brand and model of the scales used for body weight measurement in each site should be kept the same throughout the study.  $BMI = \text{Body Weight (kg)} / \text{Height (m)}^2$ .

## **7.12 Pregnancy**

The subject who becomes pregnant while receiving the study medication must immediately discontinue the study medication. Pregnancy itself is not considered as an AE, but it must be reported on the pregnancy form and submitted to the Sponsor as special safety information. The reporting time limit is the same as SAE reporting. All pregnancies must be followed up until the pregnancy outcome is obtained (e.g. spontaneous abortion, selective termination, ectopic pregnancy, full term birth, congenital anomaly). In addition, if a male subject's partner is pregnant during the study, it is also reported to the Sponsor and followed up until pregnancy completion.

Congenital anomaly, birth defects and spontaneous abortion should be reported as SAEs. Artificial abortion without complications do not need to be recorded as AEs. The pregnancy outcomes after database lock should be reported to the Clinical Drug Safety department of Sponsor. The contact information is: Email: [[contact]](mailto:[contact]), [contact], [contact]. Pregnancy report form refer to ISF.

## **7.13 Overdose**

Overdose is defined as the situation when a subject is given excessive study medication, or the subject himself /herself takes excessive study medication intentionally or accidentally and beyond the dosage defined in study protocol. Overdose is recorded on the Medication Dosing page of eCRF. If overdose is associated with any AE, it is documented on AE page of eCRF as well. If overdose is associated with any SAE, it needs to be reported according to the procedures in Section 7.3 of this protocol.

# **8. Data Management**

## **8.1 Data Traceability, Completion, and Transfer of eCRF**

Data management of the study is conducted by the data management department of dMed Biopharmaceutical Company Ltd. to assure data integrity, completeness, privacy, and traceability.

Data entry by site Investigator or the delegates must ensure the integrity and accuracy. And any correction and/or addition should be instructed to site personnel. Any correction must comply with the eCRF completion instructions.

## **8.2 Database Design**

Database is designed by the data management department of dMed Biopharmaceutical Company Ltd. per requirements of the “Code of Federal Regulations Title 21, Part 11 (21 CFR Part 11)”. Database should be able to manage the traceability of system login, data entry, data update, and data deletion. Database design should follow the CDISC standards.

## **8.3 Data Entry**

The Investigators and delegates are responsible for entering study data in eCRF. Required EDC training must be provided and completed prior to study initiation to ensure mastery of the EDC system and eCRF layout. Data entered into EDC must be validated to ensure data completeness and accuracy.

## **8.4 Data Validation**

Data validation includes programmed edit check per study design and manual review. Any discrepancy occurred during data validation must be clarified by investigator and corrected when appropriated.

## **8.5 Blinded Data Review and Breaking Blind**

The study should be unblinded at the completion of the double-blind period for all subjects. Suggested by ICH E9 Biostatistical Principles for Clinical Trials, blinded data review should be conducted before unblinding to achieve the following two purposes:

- Determine population set during blinded data review
- Review blinded study data

It should be assured that the database is locked before unblinding.

### **Emergency Unblinding**

Emergency unblinding is only applicable to emergency situations. The randomization code can only be unblinded under emergency medical conditions (e.g., treatment can only be given when the actual study treatment group of this subject is known). The investigator can discuss the potential unblinding case with the sponsor and use the IWRS system (Medidata’s Balance) to unblind the randomization code, which tells the actual treatment group that subject is randomly assigned to. If randomization code is unblinded, the time, date, and reason of unblinding must be recorded in the system, and signed off by the individual who performs the unblinding. The sponsor and Medidata staffs shall be notified immediately.

If any unexpected SAE occurs or any suspicious causality between study drug and SAE, the case should be reported immediately to regulatory agencies. Hua Medicine reserves the right to unblind the randomization code or not for such cases.

Monitor must check the blinding status of any subject at each scheduled visit to assure the blind status of each subject is intact, and/or record is complete for each emergency unblinding case.

## 8.6 Database Lock

Two stages are planned for database lock in this study.

The first database lock is scheduled at the completion of the double-blind treatment for all subjects. After the blinded data review meeting, the principle investigator, sponsor, and biostatistician must sign off all related documents before the database lock (DBL). DBL is limited to the double-blind treatment data, but not the data in the open-label treatment period. No update is permitted to locked data in principle. Errors found after DBL should be evaluated to determine whether database unlock is necessary for data correction. Documentation must be recorded if database unlock is required.

The second database lock is scheduled at the completion of the open-label treatment. A regular data review meeting is required before the final DBL. The investigator, sponsor, and biostatistician should sign off relevant documents before DBL. In principle, no update is permitted to locked data. Errors found after database lock should be evaluated to determine whether database unlock is necessary for data correction. Documentation must be recorded if database unlock is required.

## 9. Statistical Analysis

### 9.1 Sample Size Determination

This study plans to recruit 450 subjects. Considering possible drop-out of the subjects, a 20% increase of the total subjects, but no more than 564 subjects, will be enrolled. These subjects will be randomized at a ratio of 2:1 into HMS5552 treatment group or control group (placebo), i.e. no more than 376 subjects and 188 subjects are randomized to HMS5552 treatment group and control group.

Based on the planned sample size in efficacy analysis and the randomization ratio (450 subjects, HMS5552 treatment group: control group = 2:1), the study has 91.4% power to detect HMS5552 is superior to the placebo with 0.4% treatment difference (change of HbA1c from baseline at Week 24) under the assumption of type I error (alpha) at 0.05 (two sided) level and within-group standard deviation (SD) for the primary efficacy endpoint as 1.2%.

### 9.2 Analysis Population Sets

Full analysis set (FAS): Based on the intention-to-treat (ITT) analysis principle, the FAS consists of all randomized subjects who receive at least one study dose and have at least one measure of the primary efficacy endpoint post randomization.

Per-protocol set (PPS): The PPS is a subset of FAS consisting of all subjects who have no major protocol deviations. The subjects in PPS are discussed and determined in the blinded review

meeting prior to the database lock.

Safety set (SS): The SS comprises of all randomized subjects who receive at least one study dose.

The FAS is considered as the primary efficacy analysis, whereas safety assessment is performed on SS.

### **9.3 Statistical Analysis**

After all randomized subjects complete the 24-week double-blind period, the first stage database lock is performed. The study is unblinded for statistical analysis. When all subjects completed the 28-week open-label treatment period, the second database lock and statistical analysis is performed. The details of statistical analysis methods and description are provided in the separate Statistical Analysis Plan. The biostatisticians should formulate the Statistical Analysis Plan according to the clinical study protocol, should record in details the changes that deviate from the planned analysis in the protocol, and refine the final document before database lock and unblinding.

Statistical analysis will be performed using the statistical analysis software SAS version 9.2 or above. The significant level for between-group comparison is set as 0.05 (two-sided).

#### **9.3.1 Demographics and Baseline Characteristics**

The demographics is summarized for all randomized subjects (double-blind period) and those who received open-label treatment (open-label period). Summary tables or figures are used to describe the baseline characteristics between the two treatment groups. The robustness of randomization is justified by the descriptive statistics, but no statistical testing is performed on baseline characteristics.

The number and percentage of subjects who are screened, randomized (double-blind period), and received open-label treatment (open-label period) is summarized separately by study period. The primary reasons of screen failure, randomization failure and withdrawal from the study is summarized by treatment group.

For continuous variables, the descriptive statistics such as sample size, mean, standard deviation (SD), median, and range (minimum-maximum) are provided. For categorical variables, the number and percentage of subjects for each category are calculated.

The baseline characteristics are summarized for all subjects who are randomized (completed Visit 4 in double-blind period) and receive open-label treatment (completed Visit 10 in open-label period). Both the FAS and PPS populations are used for summary of baseline characteristics.

#### **9.3.2 Efficacy Analysis for Primary Endpoint**

The primary efficacy endpoint is the change of HbA1c from baseline at the end of double-blind period (at Week 24). The mixed model for repeated measures (MMRM) is used for the primary endpoint analysis. The model includes groups, visits, the interaction between groups and visit, sites, disease duration and baseline HbA1c value. Treatment difference of the mean HbA1c change from baseline at each visit is estimated by MMRM. An unstructured variance-covariance matrix is preferred in the primary model.

The adjusted least-squares mean estimate and 95% CI of treatment difference in the primary efficacy endpoint will be calculated. The following hypotheses are tested:

- Null hypothesis: at the end of double-blind treatment (Week 24), the HbA1c reduction from baseline in the two groups has no difference.
- Alternative hypothesis: at the end of double-blind treatment (Week 24), the HbA1c reduction from baseline in the two groups has significant difference.

The significant level of the between-group comparison is 0.05 (two-sided). If p value is smaller than 0.05, it is considered that the between-group difference is statistically significant. If the upper limit of the 95% CI is smaller than 0, it is considered that HMS5552 is superior to the placebo in treatment effect.

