Statistical Considerations	
Sample size
 
 
1. This study plans to recruit 450 subjects. The subject number is possible to be increased by 20% if drop-out is considered. It is estimated that the total subject number is no more than 564. Subjects are randomized at a ratio of 2:1 to the treatment group (HMS5552) or the control group (placebo), i.e. no more than 376 subjects in the treatment group and 188 subjects in the control group.
 
2. Evaluation. Study results are analyzed based on the planned sample size and randomization ratio (450 subjects, treatment group: placebo group = 2:1). A type I error level of 0.05 (two-sided) is used and standard deviation within group for primary efficacy endpoint (change of HbA1c level from baseline) is assumed as 1.2%. If the difference between treatment and control groups (treatment group-control group) is -0.4%, it can be demonstrated with 91.4% power that the efficacy for treatment group is superior to control group.
 
 
Statistical analysis
 
The primary endpoint for this study is the change of HbA1c from baseline to

	
double-blind treatment completion (Week 24). Comparison between treatment and control group is made at a significant level of 0.05 (two-sided). A mixed model for repeated measures is used for main analysis of primary endpoint. Subjects included in the analysis should have baseline measurement of the primary efficacy endpoint and at least one post treatment measurement during double-blind treatment period. The factors of the model include groups, visits, the interaction between groups and visit, sites, and baseline HbA1c value. An unstructured covariance structure is preferred for the primary analysis. The Statistical Analysis Plan prepared separately provides the details for other covariance structures in case the preferred covariance model does not converge. The primary analysis provides point estimation and 95% confidence interval for the difference in the change of HbA1c from baseline between between groups (treatment group-control group).

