## 2. Summary of Key Protocol Information

### 2.1. Changes to the Protocol Defined Statistical Analysis Plan

Protocol	SAP	Reasons
Alternative hypothesis: After 24-week treatment of HMS5552 75 mg BID, the decrease of HbA1c level in subjects with T2DM is significantly different with placebo group	Alternative hypothesis: After 24-week treatment of HMS5552 75 mg BID, the decrease of HbA1c level in subjects with T2DM is different with placebo group	“significantly” was removed, which makes SAP more accurate while no conflict with protocol.
No other efficacy endpoints in protocol.	2.2.2.3. Other Efficacy Endpoints 
 
Change of fasting insulin from baseline
 
Change of 0.5-hour postprandial insulin from baseline
 
Change of 2-hour postprandial insulin from baseline
 
Change of fasting C-Peptide from baseline
 
Change of 0.5-hour postprandial C-Peptide from baseline
 
Change of 2-hour
 
	Exploration analyses

postprandial C-Peptide  
from baseline  
• Change of HOMA- $\beta$   
from baseline  
• Change of HOMA-  
IR from baseline  
• Change of HOMA2-  
 $\beta$  from baseline  
• Change of HOMA2-  
IR from baseline  
• Change of I0/G0  
from baseline  
• Change of  
 $\Delta I30/\Delta G30$  from baseline  
• Change of  
 $\Delta C30/\Delta G30$  from baseline  
• Change of  
 $\Delta I120/\Delta G120$  from  
baseline  
• Change of  
Disposition Index (DI)  
from baseline  
• Time to  
hyperglycemia Withdraw  
• Composite HbA1c  
response rate (the  
proportion of subjects with  
HbA1c < 7.0% and without  
incidence of  
hypoglycemic events and  
no weight gain)

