## 5.2. Stratification Factors

IWRS system will be used to assign the randomization codes to unique subjects who meet randomization criteria based on stratification factors (baseline HbA1c level  $\leq 8.5\%$  or  $> 8.5\%$ ) and the block size.

Unless otherwise specified, sites will be included in models for the study analysis. Baseline of other parameters will be also included in the specified analysis.

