## 8. Primary Statistical Analyses

### 8.1. Primary Efficacy Analyses

The primary endpoint for this study is the change of HbA1c from baseline at double-blind treatment period completion (Week 24). Mixed Model for Repeated Measures (MMRM) without consideration of missing value imputation will be applied on FAS.

This model includes the factors of treatment group, visit, the interaction of visit with treatment group, pooled site, and baseline HbA1c.

Treatment group, visit, interaction of visit with treatment group, pooled site and HbA1c baseline value will be specified as the fixed effects.

An unstructured variance-covariance structure will be used for the within-subject error.

The Kenward and Roger method will be applied to estimate the degrees of freedom of the denominator.

If the model failed to converge, Heterogeneous first-order autoregressive, ARH (1), covariance structures would be adopted.

The adjusted mean difference of change from baseline between groups at fixed time points will be estimated and tested accordingly.

The primary comparison is the difference in the change from baseline in HbA1c at the end of double-blind treatment period (Week 24) between treatment groups. The point estimate and 95% CI of mean difference between treatment groups (HMS5552 75mg BID vs. Placebo BID) will be calculated. The significance level of the between-group comparison is 0.05 (2-sided). If  $p < 0.05$ , it suggests that the between-group difference is statistically significant. If the upper limit of the 95% CI is less than 0, it may be claimed that HMS5552 is superior to the placebo in treatment effect.

Below is the sample SAS code of MMRM:

```
proc mixed data=dataset;
  class TREATMENT CENTRE VISIT PATIENT;
  model CHG = TREATMENT VISIT TREATMENT*VISIT CENTRE BASELINE /
  solution ddfm=kr;
```

---

```
repeated VISIT / subject=PATIENT type=un;  
lsmeans TREATMENT*VISIT/ diff cl alpha=0.05;  
run;
```

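### The primary MMRM has two unreconciled covariate lists: protocol 9.3.2 includes disease duration, the synopsis and the SAP omit it, and SAP 2.1 does not log the change

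*Supplement*

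**What the plan says.** The primary endpoint is the change in HbA1c at Week 24, tested once at two-sided 0.05. Its model is stated in four places.

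- Protocol v1.1, 9.3.2: "The model includes groups, visits, the interaction between groups and visit, sites, disease duration and baseline HbA1c value".
- Protocol v1.1, Synopsis, Statistical Considerations: "The factors of the model include groups, visits, the interaction between groups and visit, sites, and baseline HbA1c value".
- SAP 8.1, text: "This model includes the factors of treatment group, visit, the interaction of visit with treatment group, pooled site, and baseline HbA1c".
- SAP 8.1, sample code: "model CHG = TREATMENT VISIT TREATMENT*VISIT CENTRE BASELINE".

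The LOCF sensitivity ANCOVA differs in the same way. Protocol 9.3.6 lists disease duration among its covariates and SAP 8.1.1 does not.

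Protocol 9.3 leaves the detail of the methods to the SAP, but says that the statisticians "should record in details the changes that deviate from the planned analysis in the protocol". The SAP introduction says that it rests on chapter 9 of the protocol. The change table in SAP 2.1 has two entries: a one-word edit to the alternative hypothesis, and the added endpoints ("No other efficacy endpoints in protocol"). The covariate is not mentioned. The SAP still derives diabetes duration (6.2), imputes missing diagnosis dates (6.1) and tabulates duration at baseline (7.2).

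Two further facts bear on efficiency. None of the four statements has a baseline-by-visit interaction, and the SAP pairs the model with an unstructured covariance ("An unstructured variance-covariance structure will be used for the within-subject error"). SAP 5.2 names the randomisation stratum (HbA1c up to 8.5% or above), but its commitment on model terms is: "Unless otherwise specified, sites will be included in models for the study analysis". It adds that baselines of other parameters enter where specified.

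**The concern.** Each covariate list can cite an approved document as the planned primary analysis, and neither document says which prevails if they conflict. SAP 2.1 logs a one-word edit but not the removal of a covariate from the confirmatory model. A reader therefore cannot tell whether disease duration was dropped deliberately or lost in transcription.

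What is at stake is the credibility of the one test that carries the superiority claim, whose results SAP 3.1 says go to the regulator. If the two models fell on different sides of 0.05, the sponsor could not show from the documents that the reported one was settled in advance. Protocol 9.3.3 applies the same method to FPG and 2h-PPG, so the uncertainty carries over to those endpoints.

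**Working it through.** **The plan's own figure.** Inputs from protocol 9.1 and SAP 2.4: 300 and 150 subjects, difference 0.4, SD 1.2, two-sided alpha 0.05. SE = 1.2 × √(1/300 + 1/150) = 0.120, and 0.4/0.120 = 3.33. The noncentral t with 448 df gives 91.41% (normal approximation 91.5%), so the stated 91.4% reproduces. It is a two-sample calculation without covariates and depends on neither of the terms discussed here.

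**With or without disease duration.** The documents give no correlation between duration and HbA1c change, so the partial correlation r is an assumption, ranged over 0.05 to 0.30. Duration is capped at 3 years by exclusion criterion 1. Take 1.2 as the residual SD without duration. With duration it becomes 1.2 × √(1 − r²). The two z-statistics are then bivariate normal with correlation √(1 − r²) and means δ/0.120 and δ/(0.120 × √(1 − r²)). The models disagree when exactly one exceeds 1.96 in absolute value. Free choice rejects when either does.

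| r | SD with duration | Power with duration | Disagree at 0.4 | Disagree at 0.25 | Type I error, free choice |
|---|---|---|---|---|---|
| 0.05 | 1.1985 | 91.5% | 0.6% | 1.6% | 5.2% |
| 0.10 | 1.1940 | 91.7% | 1.3% | 3.2% | 5.5% |
| 0.20 | 1.1758 | 92.4% | 2.5% | 6.5% | 5.9% |
| 0.30 | 1.1447 | 93.7% | 3.8% | 10.1% | 6.4% |

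Either model used alone keeps 5.0%.

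**One baseline slope or one per visit.** Fitting one slope b to all visits multiplies the Week-24 variance by 1 + (b24 − b)² × SD_B² / σ24², where b24 is the true Week-24 slope, SD_B the baseline SD and σ24 the Week-24 residual SD. The documents give neither the slopes nor SD_B. With σ24 = 1.2 and SD_B from 0.5 to 0.9:

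- A gap of 0.1 to 0.3 gives a ratio from 1 + 0.01 × 0.25/1.44 = 1.002 to 1 + 0.09 × 0.81/1.44 = 1.051. Power runs from 91.4% down to 90.1%.
- A gap of 0.5 gives a ratio from 1.043 to 1.141. Power runs from 90.3% down to 87.6%.

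A simulation of the unstructured MMRM (600 replicates, SD_B 0.7, about 8% missing at Week 24) gave these model-based SEs:

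| Assumed slopes, Week 4 to Week 24 | SE, one slope | SE, slope by visit | Reduction |
|---|---|---|---|
| −0.30 throughout | 0.1213 | 0.1213 | 0% |
| −0.10 to −0.40 | 0.1221 | 0.1199 | 1.8% |
| −0.10 to −0.60 | 0.1211 | 0.1153 | 4.8% |

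Mean estimates lay between −0.39 and −0.41 under both models, against a true −0.40. Where slopes diverged, the fitted common slope was about −0.09, close to the Week-4 value, so the common-slope model adjusts little at Week 24.

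**Stratum.** Continuous baseline HbA1c is in the primary MMRM (SAP 8.1), the ANCOVA (8.1.1) and the response-rate models (9.1.2, 9.1.3, 9.2.7). The FPG, PPG, C-peptide, insulin, HOMA-type and weight models (9.1.4, 9.1.5, 9.2 to 9.2.6, 9.3.5) carry the baseline of their own variable but neither baseline HbA1c nor the stratum.

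**The case against.** The strongest reply is that the SAP governs. Protocol 9.3 delegates the detail to it and requires it to be final before database lock and unblinding, and only one version exists. Section 8.1 fixes the covariates, covariance structure, fallback and degrees-of-freedom method, and gives the code. The protocol's own synopsis gives the same covariates apart from site pooling. This largely stands. A reader might infer that the primary p-value is undefined, or that the choice of model stays open after unblinding. The documents do not support that, because within the SAP there is one model. What survives is that the same section makes the delegation conditional on recording departures, and this one is unrecorded.

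A reader might also infer that the SAP introduced the single baseline slope and so loses precision at Week 24. The protocol's two statements lack the interaction as well, so there is nothing to reconcile. A common slope is a legitimate prespecified model, and the loss is zero if the slopes are equal. Nor is chance imbalance a serious worry. With an assumed baseline SD of 0.7, the imbalance has SD 0.7 × √(1/300 + 1/150) = 0.07 before stratification reduces it. A slope gap of 0.1 to 0.5 then leaves 0.007 to 0.035 points, against an effect of 0.4.

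Finally, the stratum point does not reach the primary analysis. Leaving the stratum out of the other models tends to be conservative and is not a validity fault.

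**Conclusion.** The covariate list of the sole confirmatory test is inconsistent within protocol v1.1 and between its section 9.3.2 and the SAP, and the SAP does not log the difference as the protocol requires. That rests on the text alone.

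The numerical consequence is modest and conditional on r between 0.05 and 0.30. The models disagree on significance in about 1 to 4% of trials at the planned effect, and in up to about 10% at a difference of 0.25 with r = 0.30. The type I error of 5.2 to 6.4% would arise only if someone freely chose the better result, which a single coded SAP model discourages. The item still needs closing, because the remedy is editorial and the test is the only confirmatory one.

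The baseline-by-visit term is an efficiency improvement and not the correction of an error: 0% if slopes are equal, about 2 to 5% in Week-24 SE under the assumed diverging slopes, with no average bias and no effect on the stated 91.4%. The stratum suggestion concerns secondary, exploratory and weight models only.

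**What to change.** Before unblinding:

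1. State one covariate list in the synopsis, protocol 9.3.2 and 9.3.6, SAP 8.1 and 8.1.1, and the SAS code. Either keep disease duration, which is already derived under SAP 6.2 and costs 1 df, or drop it and record the removal with its reason in SAP 2.1. State which document prevails if they differ.
2. Optionally, add BASELINE*VISIT to the MMRMs. The six post-baseline visits (Weeks 4 to 24) make this 5 df in the primary model, so 6 df with duration.
3. Optionally, add the IWRS HbA1c stratum to the FPG, PPG, C-peptide, insulin, HOMA-type and weight models.

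The cost is wording, minor changes to the model code and, for item 1, a protocol amendment or clarification. No new data are needed.
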